7.9. Known side effects

According to the SmPC equivalent provided by the manufacturer (received direct from Pfizer, Australia on 09 December 2015), which is the TGA-approved Product Information for Auralgan Ear Drops (PI-Auralgan_2015-05-07A, approved by TGA on 16 April 2014, and last updated on 03 July 2015; see Appendix 8), no known, expected side effects are associated with the use of Auralgan.

Furthermore, the known side effects associated with topical benzocaine or phenazone application reported in the Product Information are rare and considered to be "unlikely following application of Auralgan on the external ear canal".

A detailed review of the safety risks of Auralgan, specifically focusing on the risks of benzocaine-induced methaemoglobinaemia, has been conducted by the investigators (December 2015), including a review of benzocaine-associated reported adverse reactions in the United States, Australia and the UK, and no reported serious adverse reactions were identified in which Auralgan was the primary suspected causal agent. This review included a query of the Database of Adverse Events Notifications for Australia (where Auralgan has been used as an OTC medicine for at least 50 years) which includes adverse event reports between 01 January 1971 and 19 August 2015, and this found a total of 11 reports for Auralgan during the reporting period. Although neither the age of the patients or the severity of the adverse events were reported, none of the events described in these reports corresponded to our definition of a Serious Adverse Event.

All of the information provided within the 'contraindications', 'precautions', 'interaction with other medicines' and 'adverse reactions' sections of the Product Information, as well as any information identified within the review of Auralgan/benzocaine-induced methemoglobinemia as pertaining to the theoretical risks of topical benzocaine and phenazone use, has been incorporated into the trial eligibility, training and operationalisation.

For the above reasons no adverse reactions related to the IMP are expected in this trial.

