All adverse events, including any new or worsening symptoms, will be monitored in line with the trial monitoring SOP, but will only be reported if meeting the definition of a Serious Adverse Event and as per the trial Research Safety Reporting SOP (see section 8, Pharmacovigilance, below). Any SAE deemed related to the IMP will be reported as a Suspected Unexpected Serious Adverse Reaction (SUSAR) per the trial Research Safety Reporting SOP, Directive 2001/20/EC and CT-3.

Based on previous clinical experience with Auralgan no adverse events are expected in this trial, however the trial investigators wish recruiting primary care clinicians to be aware of the theoretical safety risks associated with the use of topical benzocaine and phenazone, as stated within the 'Adverse reactions' section of the Product Information, as follows:

Symptoms / signs

- Difficulty breathing
- Pale, gray or blue coloured (bluish) skin

- Severe tiredness/weakness/fatigue/inability to do physical activity
- Confusion, light-headedness, severe dizziness or headache
- Nausea, vomiting
- Dark urine
- Yellowing of the skin and the whites of the eyes (jaundice)
- Heart murmur or increased heart rate
- Enlarged spleen; enlarged liver
- Rash; urticaria; Burning/stinging/redness/new pain in or around the ears; itching/swelling (especially swelling of the ear/eye/ face/neck/throat/mouth/tongue)
- Oedema; anaphylaxis
- Vertigo; nystagmus
- Sensitisation / irritation: erythema and pruritus which may progress to vesiculation and oozing

Diagnoses

- Dyspnoea
- Cyanosis
- Methaemoglobinaemia
- Phenazone-induced haemolytic anemia and agranulocytosis
- Benzocaine toxicity
- Penetration of the local anaesthetic into the inner ear
- Benzocaine hypersensitivity reaction
- Contact dermatitis due to frequent exposure to ester-type local anaesthetics
- Angioedema

A summary of the rare complications, and recommendations for the diagnosis and treatment of benzocaineinduced methaemoglobinaemia, will be provided to clinicians within the Trial Participation Card.

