We will advise the parents/carers of participating children which adverse signs to watch for in the Parent Information Sheet (PIS), through the recruitment process (information to be provided by recruiting primary care staff to parents), in printed ear drops instructions that will be provided to parents of all participating children in the ear drops arms of the trial, and in the Trial Participation Card, which will also be given to the parents of all children receiving ear drops within the trial. With reference to a single adverse event reported in the DAEN (ref: 207569, reported on 03/05/2005), we will also advise parents to stop giving ear drops if they appear to be associated with an increase in pain.

Parents/carers will be made aware of the following:

- Auralgan may cause harm if swallowed.
- When used in small doses, no COMMON side effects have been reported with Auralgan.
- Patients are advised to tell their doctor in the event of:
 - any of these unlikely but serious side effects: burning/stinging/redness/new pain in or around the ears.
 - o any of these rare but very serious side effects: bluish skin, severe tiredness/weakness.
 - any of the following symptoms of a rare but serious allergic reaction: rash, itching/swelling (especially swelling of the ear/eye/ face/neck/throat/mouth/tongue, a condition known as angioedema), severe dizziness, trouble breathing.

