APPENDIX 8: Auralgan Product Information (PI-Auralgan_2015-05-07A)

Due to its low aqueous solubility, benzocaine is poorly absorbed and systemic toxicity is rare however, methemoglobinemia has been observed following topical application.

Indications

Auralgan ear Drops is for the effective relief of ear pain associated with otitis media.

Contraindications

Auralgan Ear Drops is contraindicated for use:

- in patients with perforated ear drums
- if discharge from the ear is present
- in patients with known hypersensitivity to any of the ingredients in the product or to similar substances

Precautions

Auralgan Ear Drops should be used with caution in patients with the following ear problems:

- Pain lasting more than 24 hours
- Fever, dizziness, stiff neck, ear discharge
- Hearing loss or ringing in the ears
- Inability to walk properly
- In patients who have had a discharge from ears, a recent ear infection or had a burst ear drum in the past.

Carcinogenesis, mutagenesis, impairment of fertility: Long-term animal studies have not been performed to evaluate the carcinogenic or mutagenic potential of Auralgan Ear Drops. The effect of Auralgan Ear Drops on human fertility is not known.

Auralgan Ear Drops should be used with caution in patients with porphyria as phenazone is possible porphyrogenic.

This product should be kept out of reach of children.

Due to a potential increased risk of methemoglobinemia, use with caution in the following patients:

- Patients taking drugs such as sulphonamides or antimalarials as these may predispose to methemoglobinemia.
- Infants under 1 year of age.
- Patients with hemoglobinopathies or Glucose-6-phosphate dehydrogenase deficiency (G6PD).

Stop use and seek immediate medical attention if you have difficulty breathing; pale, gray or blue colored skin; weakness, confusion, or headache. These may be signs of a rare, but serious condition and may appear within minutes to hours after benzocaine use.

PI- Auralgan_2015-05-07A

Use in pregnancy

The safe use of Auralgan Ear Drops during pregnancy has not been established.

Lactation

Available evidence and/or expert consensus is inconclusive or is inadequate for determining infant risk when used during breastfeeding. Therefore it is not recommended for breastfeeding mothers unless the potential benefits to the patient are weighed against the possible risk to the infant.

Interaction with other medicines

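### Section 7.9 has parents tell a doctor about possible methaemoglobinaemia signs for which the appended product information says stop the drops and seek immediate care; confusion and headache are left out

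*Protocol*

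**What the plan says.** Section 7.9 (Known side effects) states that the contraindications, precautions, interactions and adverse reactions in the product information "has been incorporated into the trial eligibility, training and operationalisation". It then gives two lists.

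- **Clinicians.** The list includes difficulty breathing, "Pale, gray or blue coloured (bluish) skin", severe tiredness or weakness, and "Confusion, light-headedness, severe dizziness or headache". Guidance on diagnosing and treating benzocaine-induced methaemoglobinaemia "will be provided to clinicians within the Trial Participation Card".
- **Parents.** The list sits under one action, "Patients are advised to tell their doctor in the event of", and includes "any of these rare but very serious side effects: bluish skin, severe tiredness/weakness". Trouble breathing and severe dizziness appear as symptoms of a serious allergic reaction. Burning, stinging, redness or new pain around the ears, rash and itching fall under the same action.

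Appendix 8 (Auralgan Product Information, Precautions) reads: "Stop use and seek immediate medical attention if you have difficulty breathing; pale, gray or blue colored skin; weakness, confusion, or headache". The next sentence gives the reason: "These may be signs of a rare, but serious condition and may appear within minutes to hours after benzocaine use".

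**The concern.** The protocol appends the product information and says it has been carried into the trial, yet the parent list gives a weaker action for the most serious signs and drops some of them. Parents are the audience that matters here. They give the drops at home, up to every 2 hours, at most 12 times a day, for at most 8 days (section 7.4), and they see any reaction first. If signs can develop within minutes to hours, a parent who has not been told to stop may give a further dose before reaching a doctor.

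The study's own contacts do not close the gap. Support calls are planned at four points (Days 1, 2, 6 and 8) and made Monday to Friday (synopsis; section 9.17), and study nurses refer health queries elsewhere (section 9.16). The investigators plainly regard the risk as real: benzocaine-induced methaemoglobinaemia is a stated reason for the 12-month lower age limit (section 6.1).

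**Working it through.** No figure in the protocol needs reproducing. The check sets Appendix 8 (Precautions) against the two lists in section 7.9, sign by sign.

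| Appendix 8 item (stop use, seek immediate attention) | Clinician list, 7.9 | Parent list, 7.9 | Action given to parents |
|---|---|---|---|
| Difficulty breathing | Present | Present, as an allergic symptom | Tell doctor |
| Pale, grey or blue skin | Present | Partial: bluish only | Tell doctor |
| Weakness | Present, as severe | Present, as severe | Tell doctor |
| Confusion | Present | Absent | None |
| Headache | Present | Absent | None |

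Counts:

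- Clinician list: 5 of 5 items present.
- Parent list: 2 of 5 present (breathing, weakness), 1 of 5 partial (skin colour), 2 of 5 absent (confusion, headache).
- Parent list items with an instruction to stop and seek immediate care: 0 of 5.

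**Is the instruction given elsewhere?** Parents are told to stop for ear discharge or suspected perforation (sections 8.2, 9.10, 9.17 and 16) and, in section 7.9, if the drops seem to increase pain. No parent-facing text gives a stop or urgent-care instruction for the signs in the table. Section 9.7 describes the Trial Participation Card as carrying emergency contact numbers, including the route for clinicians to obtain unblinding. Section 7.9 directs the card's methaemoglobinaemia guidance to clinicians.

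**Irritation.** Appendix 8 (Adverse reactions) says to discontinue promptly if sensitisation or irritation occurs. The parent list, apart from the rule on increased pain, again says only to tell the doctor. This is secondary, because the Appendix 8 sentence closes a paragraph on contact dermatitis in people frequently exposed to these anaesthetics.

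**Exposure.** Benzocaine is given only in the active arm: 501 / 3 = 167 planned children. More could be exposed if the two-arm pilot children are left out of the main analysis (sections 6.9 and 12.2) or withdrawn children are replaced (Appendix 10).

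**The case against.** The best counter-argument is that parents act on the information sheet, the printed drops instructions, the card and what site staff tell them. None of that wording is available, and it may be stronger. On this reading the section 7.9 list is a minimum, and the statement that all precautions were incorporated already commits the trial to the stop instruction. The list also conveys gravity: it calls bluish skin and severe weakness very serious, and it sets no delay before telling the doctor. The amendment history records that section 7.9 was revised on regulatory advice. Headache and confusion are hard to recognise in a one-year-old, and headache, pallor and weakness are non-specific in a febrile child.

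Part of this stands. Whether any parent would actually receive the weaker advice cannot be settled from the protocol, and copying the label word for word may not suit febrile toddlers. But section 7.9 is the text that specifies the content of those materials, and it requires no stronger wording. Calling a sign serious is not the same as saying stop and get help now. The general statement of incorporation is the claim that the parent list fails to bear out, so it cannot rescue that list. Regulatory review shows that the section was examined; it does not remove the mismatch with Appendix 8.

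**Conclusion.** The concern holds. Section 7.9 fixes a parent instruction that is less safe than the product's own labelling and conflicts with the section's statement that the precautions were carried over. None of the five Appendix 8 items has the required action, two are missing and one is partial.

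This should be corrected, with medium confidence. The conclusion assumes that the parent materials follow section 7.9. The documents give no event rate, describe the condition as rare, and report no serious reaction with Auralgan as the primary suspect, so no number of cases can be attached. Sample size, power and the planned analyses are unaffected.

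**What to change.** In the parent list of section 7.9, and in the materials it governs:

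1. State that parents should stop the drops and seek immediate medical attention for trouble breathing, pale, grey or blue skin, marked weakness, or confusion.
2. Add headache with the same action, worded as new or unusual after giving the drops.
3. State that parents should stop the drops for ear or skin irritation.
4. Check the information sheet, the drops instructions and the Trial Participation Card against this wording.

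Adverse event capture and SUSAR reporting need no change.

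The cost is a few lines and ethics approval of the wording. Because some signs are non-specific, there may be extra urgent contacts and less drop use in the two drop arms only. Those contacts could prompt antibiotic prescribing in the open primary comparison and add NHS contacts. Qualifying weakness as marked and headache as new or unusual after dosing limits this.

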7.10. Return and destruction of medication

After illness resolution (i.e. when the child's ear pain has resolved for two consecutive days without rescue analgesic medication) parents will be asked to return any used and unused ear drop bottles, with any unused contents, to the trial centre. Parents will be provided at recruitment (in the patient pack) with prepaid, return addressed secure packaging with which to do this. Once returned to the trial centre, the ear drop bottles will be

weighed and the weights recorded on the Master Drug Accountability Log. Any trial medicine that is returned will be passed from the trial centres to UH Bristol Pharmacy for destruction, in line with the current UH Bristol Pharmacy Medication Disposal SOP.

Parents will also be asked to return the containers of any used antibiotic medication that has been prescribed for the child's ear pain, to the trial centre. Parents will be provided with a further prepaid, return addressed packet (in the Patient Pack) for this purpose. When received at the trial centre, the contents of any antibiotic packaging will be checked and recorded on a trial-specific antibiotic packaging log. Any unused antibiotics will be passed to the UH Bristol Pharmacy for destruction in line with the current UH Bristol Pharmacy Medication Disposal SOP.

8. PHARMACOVIGILANCE

Safety events will be reported in line with The Medicines for Human Use (Clinical Trials) Regulations 2004.

8.1. Definitions

Adverse Event (AE)

AEs are defined as any untoward medical occurrence in a clinical trial participant. An AE does not necessarily have to have a causal relationship with the trial treatment. An AE can therefore be any unfavourable and unintended sign (including an abnormal finding), symptom or disease temporally associated with the use of a medicinal (investigational) product, whether or not related to the medicinal (investigational) product. (International Conference on Harmonisation [ICH] definition). This includes any occurrence that is new in onset or aggravated in severity or frequency from the baseline condition, or abnormal results of diagnostic procedures, including laboratory test abnormalities.

All AEs will be recorded in the Case Report Form (CRF) for the duration of the child's direct involvement in the trial. This is 8 days, i.e. the day of randomisation (Day 1) plus the 7 succeeding days. For the 10% of children whose ear pain may be unresolved by day 7, AEs will be recorded until illness resolution, which is defined as the point at which the parent-reported ear pain score for the child has been zero for two consecutive days without medication.

Serious Adverse Event (SAE)

A SAE is defined by ICH as any untoward medical occurrence that at any dose of the trial medication meets any of the following conditions:

1. Results in the death of the participant

2. Is life-threatening

The term "life-threatening" refers to an event in which the participant was at risk of death at the time of the event; it does not refer to an event which hypothetically might have caused death if it were more severe.

3. Requires in-patient hospitalisation or prolongation of existing hospitalisation

For any event that may not be immediately life-threatening or result in death or hospitalisation, but may jeopardise the participant or may require intervention to prevent one of these outcomes, the CI should exercise his/her scientific and medical judgement to decide whether or not such an event requires expedited reporting to UH Bristol (who acts on behalf of the Sponsor in these instances).

4. Results in persistent or significant disability / incapacity

Any event that seriously disrupts the ability of the participant to lead a normal life, in other words leads to a persistent or permanent significant change, deterioration, injury or perturbation of the participant's body functions or structure, physical activity and/or quality of life.

5. Is a congenital anomaly / birth defect Exposure to the trial drug before conception (in men or women) or during pregnancy that resulted in an adverse outcome in the child.

6. Other medical events

Medical events that may jeopardise the subject or may require an intervention to prevent a characteristic or consequence of a SAE. Such events are referred to as 'important medical events' and are also considered as 'serious' in accordance with the definition of a SAE.

Adverse Event Associated With the Use of the Drug

The relationship between the drug and the occurrence of each adverse event will be assessed and categorised as below. The investigator will use clinical judgement to determine the relationship. Alternative causes, such as natural history of the underlying diseases, concomitant therapy, other risk factors etc. will be considered. The investigator will also consult the relevant drug safety documentation (SmPC equivalent and/or IB).

- *Not related:* Temporal relationship of the onset of the event, relative to administration of the product, is not reasonable or another cause can by itself explain the occurrence of the event.
- Unlikely: Temporal relationship of the onset of the event, relative to administration of the product, is likely to have another cause which can by itself explain the occurrence of the event.
- **Possibly related:* Temporal relationship of the onset of the event, relative to administration of the product, is reasonable but the event could have been due to another, equally likely cause.
- **Probably related:* Temporal relationship of the onset of the event, relative to administration of the product, is reasonable and the event is more likely explained by the product than any other cause.
- **Definitely related:* Temporal relationship of the onset of the event, relative to administration of the product, is reasonable and there is no other cause to explain the event, or a re-challenge (if feasible) is positive.

*Where an event is assessed as **possibly related**, **probably related**, or **definitely related** the event is an *adverse* reaction.

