8.2. Procedure for reporting

All adverse event reporting will be in accordance with the UH Bristol 'Research Safety Reporting Policy' (http://www.uhbristol.nhs.uk/media/2518477/research_safety_reporting_sop_009_uhbristol_r_i_v8.0_19.10.1 5.pdf. A formal SOP and flowchart will be developed to describe the reporting procedure in detail.

All Adverse Events

All AEs will be reported by the Chief Investigator from the time a signed and dated informed consent form is obtained until completion of the patient follow-up at 28 days after randomisation. Adverse events described in the Patient Information Sheet, Protocol or in the pharmacological documentation associated with the trial drug will be monitored and recorded as non-reportable. This includes the potential incidence of tympanic membrane perforation, which may occur in up to 7% of children with AOM. The trial training and recruitment processes will be carefully designed to ensure that clinicians and parents will be vigilant to this potential problem, and parents will receive training to immediately recognise the signs that tympanic membrane perforation may have occurred (discharge from the ear, and/or sudden relief of the child's ear pain), and know what to do (stop treatment with ear drops).

If a Responsible Clinician or other member of the research team becomes aware that a trial-related SAE has occurred beyond the 28 day period this will also be reported to the Sponsor. Those occurrences meeting the definition of SAEs must be reported using the Serious Adverse Event Form, including any related SAE which a Responsible Clinician believes has occurred beyond the trial follow-up period). UH Bristol, on behalf of the Sponsor, will evaluate any safety information that is spontaneously reported by a CI.

All AEs, regardless of seriousness, severity, or presumed relationship to trial drug, must be recorded in the source document and the CRF, together with any measures taken. All Centre PIs must record in the CRF their opinion concerning the relationship of the adverse event to trial therapy. UH Bristol, on behalf of the Sponsor, assumes responsibility for overseeing the appropriate reporting of serious adverse events to the regulatory authorities, in line with the SLA.
All emerging pharmacovigilance data which may be related to activities carried out by the IMP and placebo supplier will be notified to the supplier.

Serious Adverse Events (SAEs)

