- Baseline sociodemographic factors: parental occupation, child's ethnicity, maternal smoking habits, number of other children in the child's home, and whether the child was breastfed at 3 months (the rationale for collecting these data at this point is also to reduce the pressure on recruitment within the GP consultation);
- The child's daily parent-rated ear pain score (average over the preceding 24 hours);
- Children aged five years and above will be asked to rate their own ear pain;
- Presence of any ear discharge (if yes, parent will be advised to stop using ear drops immediately);
- Number of doses of ear drops administered, and to which ears;
- Whether the child has taken any antibiotics by mouth today;
- Number of doses of rescue analgesia administered;
- Parent's rating (mild, moderate or severe) of the child's other symptoms over the preceding 24 hours, including: episodes of distress or crying; disturbed sleep; interference with normal activities of daily living; eating or drinking less than normal; fever; hearing problems; any other symptoms (potential adverse events);
- Has the child missed any school, nursery or childcare today
- Has the parent or carer lost time from work today

On the Day 1 telephone call, the Research Nurse will remind the parent to complete the CHU-9D quality of life questionnaire for their child on the following day, at 24-36 hours post recruitment – i.e. on Day 2.

Days 2-7: parents will receive another two calls, at their convenience, to support them in completing the first week of the daily Symptom and Recovery Questionnaire. The calls will guide the parent through the daily Symptom and Recovery Questionnaire and transcribe the data collected over the phone onto the 'office use' shadow Symptom and Recovery Questionnaire at the trial centre. The information for which the Nurse will ask the parent for each day is as follows:

- Day 2 only: Child's quality of life over the previous 24 hours using the CHU-9D validated questionnaire;
- The child's daily parent-rated ear pain score (average over the preceding 24 hours);
- Children aged five years and above will be asked to rate their own ear pain;
- Presence of any ear discharge (if yes, parent will be advised to stop using ear drops immediately);
- Number of doses of ear drops administered (up to a maximum number of 8 days), and to which ears;
- Whether the child has consumed any antibiotics by mouth today;
- Number of doses of rescue analgesia administered;

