9.20. Telephone follow-up post Day 8 (for children with ongoing ear pain)

For children whose ear pain is still rated by the parent at >0 after seven days post-randomisation, we will ask the parent's permission to continue to contact them by telephone twice weekly until the child's ear pain resolves (i.e. until the child is free of ear pain for two consecutive days without medication), of which one call at the end of that week to ask them about their healthcare resource use during the week.

These calls will take place for each week during which the child has experienced ongoing ear pain and until illness resolution (i.e. for ear pain ongoing after Day 8, up to Day 15; for ear pain ongoing after Day 15, up to Day 22, etc) up to a maximum of four weeks. We anticipate that the 'additional' mid-week telephone interview is anticipated to take no more than 5 minutes per week, and the additional end-of-week telephone interview will last no longer than 10 minutes. We anticipate that these 'additional' telephone interviews will be conducted in around 10%17 of children taking part in the study.

The purpose of the mid-week telephone interview, until the child's ear pain resolves, will be to ask the parent:

- The child's parent-rated ear pain score at the point of the telephone call (average over the preceding 24 hours);
- Number of doses of ear drops administered, and to which ears;
- Whether the child has consumed any antibiotics by mouth today;
- Number of doses of rescue analgesia administered.

• Collect resource use data (once at the end of the week).

At the end-of-week telephone call the parent will be asked about the family's use of healthcare resources as a result of the child's ear pain, including:

- Visits to GP, WIC or OOH
- Use of hospital-related services including CED
- Use of NHS telephone service 111 (or equivalent)
- Use of prescription medicines
- Purchase of over-the-counter medicines
- Loss of parent or carer's time from work
- Loss of child's time from nursery, childcare or school

IF the ear pain stops before or by the mid-week phone call, then the resource use questions due at the end of week phone call can be asked as a round up at the mid-week call to avoid calling parents again whose children are now well. In other words, we will ask them what resources they have used as a round-up UP TO the point in the week when the ear pain stopped (as long as that is by the time of the mid-week call).

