Post Day 8 (Trial Nurse/Administrator telephone call): Parents whose children are still experiencing ear pain at after 7 days following the day of randomisation will continue to be telephoned twice weekly in order to identify the date on which the child's parent-reported ear pain had resolved for two consecutive days, without analgesic medication. We estimate that 10% of children will still be symptomatic at this point (Day 8)¹⁷. Parents will be asked to score their child's ear pain (on average over the preceding 24 hours) and to report any oral antibiotic or analgesic consumption.

Month 3 (primary care notes review and postal/ telephone questionnaire) will include: primary care notes review for primary and secondary care attendances, and Serious Adverse Events and a postal/telephone questionnaire to collect CHU-9D and OMQ-14, following which the study team will send the parent a £5 voucher.

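### Section 8.1 promises adverse-event recording until illness resolution, but the calls after Day 8 ask about neither new symptoms nor ear discharge

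*Protocol*

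**What the plan says.** **The window.** Section 8.1 defines the standard period for recording adverse events in the CRF: "This is 8 days, i.e. the day of randomisation (Day 1) plus the 7 succeeding days". It then extends the period for children still in pain: "For the 10% of children whose ear pain may be unresolved by day 7, AEs will be recorded until illness resolution". Resolution means a parent-rated pain score of zero on two consecutive days without medication. Section 10.2, under Days 1 to 8, lists adverse events among the daily items and has parents continue those items until two days of symptom resolution. Section 8.2 gives a different end point, with the Chief Investigator reporting all adverse events "until completion of the patient follow-up at 28 days after randomisation".

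**Collection on Days 1 to 8.** Section 9.17 has a daily ear-discharge item, "Presence of any ear discharge (if yes, parent will be advised to stop using ear drops immediately", and an open item on other symptoms that the protocol labels as possible adverse events.

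**Collection after Day 8.** Section 9.20 describes twice-weekly calls, with the parent's permission, for at most four weeks. It says that parents complete no further questionnaire. It introduces the mid-week list with "The purpose of the mid-week telephone interview, until the child's ear pain resolves, will be to ask the parent". The items are pain score, "Number of doses of ear drops administered, and to which ears", oral antibiotics and rescue analgesia. At the end-of-week call "the parent will be asked about the family's use of healthcare resources as a result of the child's ear pain", together with time lost from work, school or childcare. The Post Day 8 entry in section 10.2 is shorter: "Parents will be asked to score their child's ear pain (on average over the preceding 24 hours) and to report any oral antibiotic or analgesic" use.

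**The concern.** The protocol makes a specific safety-recording commitment for a named subgroup, then fixes the content of the only scheduled calls in that period, and the two do not match. Staff who follow 9.20 to the letter would not meet 8.1.

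Adverse events are a listed secondary outcome (section 11). Ear discharge is the sign by which parents are taught to recognise a possible perforation (sections 8.2 and 16), which the protocol says may occur in up to 7% of children with acute otitis media. If nobody asks, an absence of non-serious events after Day 8 cannot be told apart from an absence of data.

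**Working it through.** The plan states no figure to reproduce. The check sets the collection lists side by side and then counts the children affected.

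**Step 1. What each list contains**

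| Item | Days 1-8 (9.17) | Calls after Day 8 (9.20) | Post Day 8 entry (10.2) |
|---|---|---|---|
| Parent-rated ear pain | daily | mid-week | listed |
| Ear-drop doses and which ear | daily | mid-week | not listed |
| Oral antibiotics | daily | mid-week | listed |
| Rescue analgesia | daily | mid-week | listed |
| Ear discharge | daily | **absent** | **absent** |
| Any other symptoms (possible adverse events) | daily | **absent** | **absent** |
| Health-service contacts and medicines | Day 8 | end of week | not listed |
| Time lost from work or school | daily | end of week | not listed |

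The two items that would deliver the 8.1 commitment are the two that bear most directly on adverse events, and neither is carried forward. Section 10.2 says that the daily recording, adverse events included, runs to two symptom-free days, but 9.20 stops the questionnaire at Day 8.

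**Step 2. Other routes for an event after Day 8**

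- End-of-week call (9.20): GP, walk-in, out-of-hours, hospital and 111 contacts, and medicines, arising from the ear pain. An event shows only if care or medicine was sought for the ear.
- Primary care notes review: section 10.2 (Month 3) lists attendances and serious adverse events. Section 16 describes it more widely, as a source of adverse events including serious ones. On either reading it holds only what reached a clinician.
- Hearing: section 16 has records monitored for deafness, and the OMQ-14 at 3 months includes the parent's view of the child's hearing.

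What no route covers is the non-serious event that the parent notices and never takes to a clinician.

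**Step 3. How many children**

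Inputs: 501 children, 167 per arm (section 12.1); 10% unresolved (sections 8.1 and 9.20). The day 7 in 8.1 is read as seven days after randomisation, which is Day 8 in the protocol's numbering.

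- All arms: 501 × 0.10 = 50.1, about 50.
- Two drop arms: 2 × 167 = 334; 334 × 0.10 = 33.4, about 33.
- No-drop arm: 167 × 0.10 = 16.7, about 17.

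If the planned 20% attrition applied equally to these children (an assumption), the counts would be 0.8 × 50.1 ≈ 40 and 0.8 × 33.4 ≈ 27. The protocol gives no rate for refusal of further calls, so no lower bound can be set.

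**The case against.** The strongest case against is that little is lost. Section 7.4 limits drops to 8 days, so on that reading the later period is off treatment. Serious and medically attended events have the routes in Step 2. Parents are trained to watch for discharge and hold the study team's contact details. Sections 7.9 and 8.2 leave monitoring and reporting procedures to SOPs.

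Most of this stands, and it rules out four stronger readings that a reader might infer:

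- **That these children are still being dosed, and so are the most exposed.** This rests on the dose item in 9.20, which conflicts with the 8-day maximum in 7.4. The conflict must be reconciled; neither side can be taken as settled. About 17 of the 50 children would be in the no-drop arm.
- **That a comparison of safety between arms after Day 8 would look falsely clean.** The protocol specifies no such comparison. Section 11 ties the adverse-event outcome to the questionnaire with telephone support, and the questionnaire ends at Day 8.
- **That hearing problems would go unasked.** Section 16 provides records monitoring and the 3-month OMQ-14.
- **That 8.2 promises to question every parent to Day 28.** Its 28 days is a reporting period for the Chief Investigator, and 7.9 says that only serious events are reported. It conflicts with the window in 8.1, but it is not a clear undertaking to contact the other 90% of families.

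The objection does not remove the contradiction itself. The commitment in 8.1 depends on persisting pain, not on continued dosing. An SOP could add the missing questions, but only by going beyond call content that the protocol itself sets out.

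**Conclusion.** The point holds as an internal contradiction with a limited consequence. Carried out as written, the plan does not deliver the adverse-event recording that 8.1 and 10.2 promise for children whose pain persists. The gap is in data capture, not in the instructions given to parents. It is confined to non-serious events that never reach a clinician, in at most about 50 of 501 trial children (about 33 of 334 in the drop arms).

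This size rests on the protocol's 10% applying equally across arms, on full recruitment, and on call lists used as printed. It is stated before attrition and refused calls. Because the remedy is cheap, the amendment is worth making, but nothing here bears on the primary or key secondary analysis.

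**What to change.** 1. Add two existing data items from 9.17 to the call list in 9.20 and to the Post Day 8 entry in 10.2: any other new symptoms, and presence of any ear discharge.
2. Reconcile the window in 8.1 (8 days, or resolution if later) with the 28 days in 8.2, so that the stated window matches what is collected. The wording should recognise that the calls need permission and end after four weeks, so resolution is not always reached.
3. Reconcile the scope of the notes review in 10.2 (attendances and serious events) with section 16 (adverse events including serious ones).
4. Reconcile the 8-day maximum in 7.4 with the drop-dose item in 9.20. Any advice to parents that accompanies the discharge item after Day 8 follows from that reconciliation and is for the sponsor to settle; no clinical rule is proposed here.

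The cost is a minute or two more per call and aligned wording in 7.4, 8.1, 8.2, 9.20, 10.2 and section 16. There is no extra contact and no change to the sample size.
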